2. OBJECTIVES

Primary Objective:

To assess patient satisfaction of light trauma care in the primary and secondary care setting.

Secondary Objective(s):

In addition, we aim to study demographic factors, treatment results, time consumption and costs to assess which determinants are responsible for the patient satisfaction.

3. STUDY DESIGN

This is an observational cohort study including patients presenting at the X-ray facility in the general practice Zorgplein Lemmer and patients presenting at the X-ray facility of the Antonius Hospital Sneek, with an X-ray confirmed diagnosis of a non-complex fracture or dislocation and planned to be treated in either the Zorgplein Lemmer or Antonius Hospital Sneek. Patients aged 11 years or younger, and/or presenting outside ordinary business hours are excluded, due to possible inclusion bias. After inclusion the follow-up questionnaires continue for 12 weeks. The total duration of the study is 18 months.

4. STUDY POPULATION

4.1 Population (base)

The base population consists of patients in the region around Lemmer and Sneek.

4.2 Inclusion criteria

Eligible patients must meet the following inclusion criteria:

1. X-ray confirmed diagnosis of a non-complex fracture or dislocation, which can be treated in the primary care setting according to the treatment protocol.
2. Ability of the patient or assigned representative to understand the content of the patient information/informed consent form.
3. Signed and dated written informed consent. Parents of patients of age 12-17 must provide a signed and dated written informed consent as well.

4.3 Exclusion criteria

1. Age 11 years and younger.
2. Patients presenting outside ordinary business hours.

4.4 Sample size calculation

The sample size calculation has been performed based on the difference in patient satisfaction. There was no literature available concerning patient satisfaction in trauma care in general practices or hospitals. Therefore, we based our sample size calculation on an estimated effect size. With a significance level of 5%, a power of 80% and equal treatment groups, a sample size of 200 patients (100 per group) was calculated. This sample size will allow us to demonstrate effect sizes of 0.4 (small to medium) or over.

5. TREATMENT OF SUBJECTS

5.1 Investigational product/treatment

Treatment in the general practice is identical to treatment in the hospital and is equal to the national guidelines. Those are described in the online treatment protocol 'Behandelprotocollen Lichte traumazorg in de eerste lijn'. This study has no impact on speed, choice, location or execution of diagnostics or treatment and thus is an observational study.

5.2 Use of co-intervention

Patients are allowed to ask treatment next to the treatment according to the treatment protocol.

6. METHODS

6.1 Study parameters/endpoints

6.1.1 Main study parameter/endpoint

Patient satisfaction measured using the Patient Satisfaction Questionnaire Short Form (PSQ-18; 12 weeks after treatment).

Marshall GN Hays RD. The Patient Satisfaction Questionnaire Short-Form (PSQ-18). Santa Monica, CA: RAND, 1994.

6.1.2 Secondary study parameters/endpoints

1. Patient satisfaction measured using the PSQ-18 (1 and 6 weeks after treatment).

Marshall GN Hays RD. The Patient Satisfaction Questionnaire Short-Form (PSQ-18). Santa Monica, CA: RAND, 1994.

2. Complications of treatment and pain scores (12 weeks after treatment).
3. Physical functioning according to the 12-item World Health Organisation (WHO) Disability Assessment Schedule II (12 weeks after treatment).

*World Health Organization Disability Assessment Schedule II (WHO-DAS II)
WHO, Geneva (2000) www.who.int/icidh/whodas/whodasversions/12int.pdf*

4. Limitations in functions of upper extremities (if applicable) according to the Disabilities of the Arm, Shoulder and Hand (DASH) questionnaire (12 weeks after treatment).

5. General health status according to the 12-item General Health Questionnaire (GHQ-12; 12 weeks after treatment).

Goldberg, D. P. (1972). The Detection of Psychiatric Illness by Questionnaire. Maudsley Monograph No. 21. Oxford University Press: Oxford.

6. Quality of life using the EQ5D questionnaire (12 weeks after treatment).

Euroqol Group (1990) Euroqol—a new facility for the measurement of health-related quality of life. Health Policy 16:199–208

7. Time consumption (waiting time, treatment time, travelling time and distance; 1, 6, and 12 weeks after treatment).

8. Costs (12 weeks after treatment).

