Study population: 200 patients (≥ 12 years old) with fractures or dislocations which are non-complex such that they can be treated in the primary care setting. This sample size will allow us to demonstrate effect sizes of 0.4 (small to medium) or over with 80% (beta 20%) power using a two-sided alpha of 0.05.

Determinants: demographic factors (age, sex, comorbidity), nature of the trauma, treatment setting (in general practice or in the hospital, distance to treatment center), treatment results (functionality scores, complications, general health, quality of life), time consumption and costs.

Main study parameters/endpoints:

Primary:

- Patient satisfaction (questionnaires after 1, 6, and 12 weeks)

Secondary:

- General health (GHQ questionnaire), age, SES (after 1 week)
- Complications (e.g. secondary dislocation and pain scores; questionnaire after 12 weeks)
- Physical function (questionnaire after 12 weeks)
- Time consumption (questionnaires after 1, 6, and 12 weeks)
- Costs (economic evaluation; questionnaire after 12 weeks).

Nature and extent of the burden and risks associated with participation, benefit and group relatedness:

Since this is an observational study using a limited number of questionnaires in patients who receive regular care, there is no risk associated with participating in this study. The burden for participating patients will very low because they will only be asked to fill in a few questionnaires, which take about one and a half hours in total to fill in.

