1. INTRODUCTION AND RATIONALE

In the Netherlands, diagnostics and treatment of bone fractures and dislocations are generally organized in the secondary care setting. When a fracture or dislocation is presumed, most general practitioners refer the patient to an X-ray facility in a nearby hospital. When the fracture or dislocation is confirmed, an emergency care doctor or trauma surgeon generally provides the treatment and follow-up. In contrast, since January 2017 the general practice 'Zorgplein Lemmer' provides equal care for patients with non-complex fractures or dislocations. In this practice, regular X-ray diagnostics are used, which are digitally transmitted to the radiologist. When a non-complex fracture or dislocation (a so-called 'light trauma') is diagnosed, the for this purpose well-trained general practitioners provide the patient with the usual care (e.g. a splint or sling) and provides follow-up consults in his practice. While light trauma care is provided in several general practices in the Netherlands and healthcare professionals in both the general practice and the hospital are very satisfied with this provided care, it is unknown what the patient satisfaction level is and which determinants affect this patient satisfaction. Nowadays, substitution of care from the secondary to the primary care setting is stimulated by the government and insurers and in that light we aim to study the patient satisfaction of light trauma care for non-complex fractures or dislocations in the primary care setting in comparison to the secondary care setting. When the general practitioners in our study obtain similar results as the nearby hospitals, light trauma care may be substituted nationwide and beyond.

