6.1.3 Other study parameters

Baseline data: age, gender, social economic status, location and severity of the trauma (1 week after treatment).

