8.3 Cost-effectiveness

The proposed cost–utility analysis will use decision modeling and sensitivity analysis techniques to ensure the robustness of the study's conclusions. Cost-effectiveness will be assessed using the incremental cost-effectiveness ratio, which is determined by calculating the difference in costs divided by the difference in QALYs between both treatment groups.

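### EQ-5D is measured only at 12 weeks, so the trial's own data cannot give the QALY difference that the cost-utility analysis needs

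*Combined protocol and SAP*

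**What the plan says.** Section 8.3 states that the cost-utility analysis "will use decision modeling and sensitivity analysis techniques". It defines the incremental cost-effectiveness ratio (ICER) by "calculating the difference in costs divided by the difference in QALYs between both treatment groups". It does not say how QALYs are computed, which value set is used, or where any utilities other than the trial's own would come from.

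EQ-5D is the only utility instrument in the plan. Section 6.1.2 item 6 reads: "Quality of life using the EQ5D questionnaire (12 weeks after treatment". No other section adds an earlier assessment:

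- Section 6.1.3 lists "Baseline data: age, gender, social economic status, location and severity of the trauma (1 week after treatment", which contains no utility measure and is itself collected at week 1.
- The Summary names quality of life only as a determinant, with no time point. It places the GHQ at week 1, but no conversion of GHQ scores to utility is planned.

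Contacts at the missing times already exist. The Summary lists "Patient satisfaction (questionnaires after 1, 6, and 12 weeks", and section 6.1.2 item 1 reads "Patient satisfaction measured using the PSQ-18 (1 and 6 weeks after treatment". Item 7 (time consumption) also uses weeks 1, 6 and 12.

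**The concern.** A QALY is utility summed over time. The horizon is 12 weeks of recovery from an acute injury, and the schedule observes utility only at its end. A difference between settings during the early weeks could be gone by week 12. If the analysis then uses the week-12 EQ-5D without imported utilities, that difference counts as zero. If it imports utilities or assumes a path, the denominator rests on that choice rather than on what these patients reported. Because the groups are not randomised (section 6.2), outside values cannot by themselves show how these two groups differ during recovery.

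The loss is permanent: once a patient has passed weeks 1 and 6, those utilities cannot be recovered. The analysis also bears on the protocol's case for moving this care into general practice.

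A second, conditional point concerns the ratio. The rationale in section 1 envisages the case "When the general practitioners in our study obtain similar results as the nearby hospitals". If that happens, the QALY difference may be near zero and the ICER unstable. The plan does not state this as an expectation.

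**Working it through.** **The plan's own figure.** The documents give no figure for QALYs or the ICER. The only related number is the sample size in section 4.4: 200 patients, 100 per group, for an effect size of 0.4 in satisfaction at two-sided 5% and 80% power. It reproduces: 2 × (1.960 + 0.842)² / 0.4² = 98.1, so 99 per group and 198 in total. It was not set with QALYs in mind and does not change here.

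**Inputs from the documents.** Horizon 12 weeks (section 3); EQ-5D at week 12 only (6.1.2 item 6); existing contacts at weeks 1, 6 and 12 (6.1.2 items 1 and 7); 100 per group (4.4). All utilities, SDs and correlations below are assumptions.

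**Step 1: how much of the QALY is observed.** The most that can accrue is 12/52 = 0.231 QALY. With EQ-5D at weeks 1, 6 and 12, trapezoids between visits, and week 1 carried back over week 0–1, the difference is

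(3.5·d1 + 5.5·d6 + 3·d12) / 52,

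where d1, d6 and d12 are the between-group utility differences at the three visits. The weights are 3.5/12 = 29.2%, 5.5/12 = 45.8% and 3/12 = 25.0%. The current schedule observes only the last.

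**Step 2: size of a transient difference.** Let a difference d last to week 6 and fall linearly to 0 at week 12. Over weeks 0–12 it is worth d × (6 + 3)/52, and over weeks 1–12 d × (5 + 3)/52.

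| d | Weeks 1–12 | Weeks 0–12 | Week-12 value alone |
|---|---|---|---|
| 0.03 | 0.0046 | 0.0052 | 0 |
| 0.05 | 0.0077 | 0.0087 | 0 |
| 0.10 | 0.0154 | 0.0173 | 0 |

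The last column is 0 by construction. The table shows how much QALY difference is compatible with seeing nothing at week 12.

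**Step 3: the sign can reverse.** Take differences of −0.10, −0.05 and +0.02 at weeks 1, 6 and 12.

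- Three visits: (−0.35 − 0.275 + 0.06)/52 = −0.0109.
- Week 12 only, constant path: 12 × 0.02/52 = +0.0046.
- Week 12 only, linear from an equal start: 6 × 0.02/52 = +0.0023.

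**Step 4: precision after adding weeks 1 and 6.** SE = SD × √(w′Rw)/52 × √(2/100), where R has a common correlation ρ. For weights (2.5, 5.5, 3), covering weeks 1–12, w′Rw = 45.5 + 75.5ρ. For (3.5, 5.5, 3), with carry-back, it is 51.5 + 92.5ρ.

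- Lowest (SD 0.15, ρ 0.3, weeks 1–12): SE 0.0034, 95% half-width 0.0066.
- Middle (SD 0.20, ρ 0.5): SE 0.0050 for weeks 1–12, 0.0054 with carry-back.
- Highest (SD 0.25, ρ 0.7, carry-back): SE 0.0073, 95% half-width 0.0144.

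These assume complete data on 200 patients and no covariate adjustment.

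**Step 5: the week 0–1 assumption.** For differences of 0.10, 0.05 and 0 at weeks 1, 6 and 12, carry-back gives 0.0120. Setting the week-0 difference to zero gives 0.0111; setting it to twice the week-1 value gives 0.0130.

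**Step 6: conditional instability of the ratio.** The probability that the estimated QALY difference has the wrong sign is Φ(−D/SE), where D is the true difference. D = 0.0043 corresponds to d = 0.025 over weeks 0–12.

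| D | SE 0.0035 | SE 0.005 | SE 0.007 |
|---|---|---|---|
| 0.0043 | 11% | 20% | 27% |
| 0.0087 | 1% | 4% | 11% |
| 0.0173 | <1% | <1% | <1% |

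**The case against.** The strongest reply is that section 8.3 plans a decision model. Such a model can take events observed in the trial, attach published utilities to health states, and produce a QALY difference without repeated EQ-5D. On that view the gap is an unnamed utility source and model structure, not a flaw in the schedule. This stands in part: a modelled figure is possible, and the finding is limited to what the trial's own data can estimate. But the complications, pain and function measures that could drive such a model (6.1.2 items 2 to 4) are also scheduled only at 12 weeks, and sensitivity analysis can vary an assumption but not replace missing observations.

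Section 5.1 says treatment is the same in both settings, which makes large early differences, such as 0.10 for six weeks, less plausible. That is a fair caution about the upper scenarios. It does not exclude differences from case mix or follow-up, and it supplies no utilities.

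The proposed change is also not a complete remedy. Week 0–1 stays unmeasured, there is still no pre-treatment utility, and the SEs above are optimistic if data are missing. All of this stands.

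Finally, cost-utility is not a stated objective in its own right: section 2 treats costs as a possible determinant of satisfaction. That limits the importance of the point but does not remove it, because section 8.3 commits to the analysis.

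**Conclusion.** The concern holds. Followed exactly, the plan leaves the between-group QALY difference over 12 weeks unmeasured, and any ICER would depend on unnamed outside utilities or an assumed path. Under the three-visit weighting, 75% of the QALY weight falls on visits without EQ-5D. Early differences of 0.03 to 0.10 in utility, worth roughly 0.005 to 0.017 QALY, could pass unseen; these values are illustrative. With the added visits, differences of this size become estimable but imprecise. The ICER instability is a secondary risk that applies only if the true QALY difference is small. The primary PSQ-18 comparison and the sample size are unaffected. This should be fixed, and before patients pass weeks 1 and 6.

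**What to change.** - **Section 6.1.2 item 6:** collect EQ-5D in the existing 1-, 6- and 12-week questionnaires.
- **Section 8.3, QALYs:** compute them as area under the curve over follow-up. State the value set, the handling of missing EQ-5D, and the rule for week 0–1 (for example, week-1 value carried back, with a week 1–12 sensitivity analysis).
- **Section 8.3, adjustment:** adjust for the section 6.1.3 baseline variables. Do not adjust for the week-1 EQ-5D as if it were baseline, because it is taken after treatment.
- **Section 8.3, model:** state what the decision model adds and the source of any outside utilities.
- **Section 8.3, reporting:** report incremental net monetary benefit with a bootstrap 95% CI alongside the ICER. This needs a stated willingness-to-pay threshold or range, which the documents do not give.
- **Optional:** an EQ-5D at inclusion would allow adjustment for baseline utility. It would be a new data-collection point, since even the baseline data are collected at week 1.

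The core change costs a few extra items per patient at two existing contacts, slightly more missing data to handle, new wording in 8.3, and perhaps a small update to the 1.5-hour burden statement in the Summary and section 9.3. It needs no extra visits or patients.

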The assessment of eligibility will be performed by participating general practitioners near Lemmer, who will approach each potential study patient and inquire about their interest and eligibility in participating in this study. Both the Zorgplein Lemmer as well as the Antonius Hospital Sneek will be informed and trained about the importance of recruiting consecutive patients. If the patient wishes to participate, a legally eligible member of the research team or staff will go through the informed consent process, explaining the purpose of the study, procedures, risk/benefits, alternatives to participation and data protection. Each patient choosing to participate will sign and date an informed consent form. Parents of participants of age 12-17 years old at the date of informed consent must provide a signed and dated written informed consent as well. A copy of the signed informed consent form(s) will be placed into the patient's medical record and the investigator site file and one copy will be handed over to the patient. All patients with written informed consent will be allocated to a unique patient study number. The date of informed consent and the recruitment information is entered in the study database. All patients who commence treatment within the study are considered as enrolled and all enrolled patients should be followed up within the study, except if their study participation is prematurely terminated. All patients recruited in the Zorgplein Lemmer or Antonius Hospital Sneek are automatically allocated to the Zorgplein Lemmer and Antonius Hospital Sneek analysis group, respectively.

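### The travel difference between practice and hospital is confounded with place of residence to an unknown degree, and no residence is recorded to separate the two

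*Combined protocol and SAP*

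**What the plan says.** Travel appears twice in the plan. Section 6.1.2 lists it within secondary endpoint 7: "Time consumption (waiting time, treatment time, travelling time and distance; 1, 6, and 12 weeks after treatment". The Summary also names "distance to treatment center" among the determinants, under treatment setting. Costs are a separate endpoint, given only as "Costs (12 weeks after treatment", with no cost items.

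On who is compared, section 4.1 states: "The base population consists of patients in the region around Lemmer and Sneek". Section 6.3 forms the groups by place of recruitment: patients are "automatically allocated to the Zorgplein Lemmer and Antonius Hospital Sneek analysis group, respectively". Two other statements in section 6.3 bear on where the hospital patients come from. One is "The assessment of eligibility will be performed by participating general practitioners near Lemmer". The other is "Both the Zorgplein Lemmer as well as the Antonius Hospital Sneek will be informed and trained about the importance of recruiting consecutive patients".

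The baseline list in section 6.1.3 reads: "Baseline data: age, gender, social economic status, location and severity of the trauma (1 week after treatment". The location there is that of the injury. Neither home address nor distance to the facility not attended is listed.

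Section 8.2 starts with univariable tests of outcome scores between the two groups. Its multivariable models have satisfaction as the outcome, with time consumption as one possible predictor. No model has travel as its outcome.

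**The concern.** The rationale (section 1) is that care may be moved from hospital to general practice if results are similar. For travel, the quantity that informs this is what the same patient would travel to the practice and to the hospital. The plan records the trip actually made, by two groups sorted by the site that recruited them. The two quantities agree only if both groups live in the same area, and the plan neither requires nor checks that.

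If the hospital group includes many people living near Sneek, their trips are short and the travel saving from local care shrinks or disappears, although nothing about either facility has changed. Less travel is a plausible benefit of care near home, so a diluted or even reversed result could mislead on a named endpoint. If travel costs are counted, the same distortion would pass into the cost difference used in section 8.3, for which no adjustment for residence is stated.

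**Working it through.** **The plan's own figure.** The documents give no figure for travel. The only figure to reproduce is the sample size in section 4.4. For a standardised effect of 0.4, two-sided alpha 0.05 and 80% power, the normal approximation gives 99 per group, 198 in total. The t-test calculation gives 99.1 per group, with power 0.804 at 100 per group. The stated 200 is reproduced. It concerns satisfaction and has no bearing on this point.

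**Model.** The documents give no distances and no residence mix, so all inputs below are assumptions.

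- The trip between the Lemmer area and Sneek is 1 unit.
- A local trip, from home to the facility in one's own area, is a.
- s is the share of the hospital group living near Sneek.
- At first, the whole practice group lives near Lemmer.

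**Formulas.**

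- Mean trip, practice group: a
- Mean trip, hospital group: s × a + (1 - s) × 1
- Observed difference, hospital minus practice: s × a + (1 - s) - a = (1 - s)(1 - a)
- Difference for the same Lemmer-area patient: 1 - a
- Ratio of observed to same-patient difference: 1 - s, whatever the value of a

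**Results with a = 0.25** (same-patient difference 0.75):

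| s | Observed difference | Share of same-patient difference |
|---|---|---|
| 0 | 0.75 | 100% |
| 0.25 | 0.5625 | 75% |
| 0.5 | 0.375 | 50% |
| 0.75 | 0.1875 | 25% |
| 1 | 0 | 0% |

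The shares are the same at a = 0.1 and a = 0.5. In kilometres, if the extra trip to the hospital for a Lemmer-area patient were 20 km (assumed), the reported difference would be 20 km at s = 0, 10 km at s = 0.5 and 0.2 × 20 = 4 km at s = 0.8.

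**Some practice patients living near Sneek.** If g is their share, the observed difference becomes (1 - s - g)(1 - a). With a = 0.25 and g = 0.1 this is 0.675 at s = 0, 0.3 at s = 0.5, and -0.075 at s = 1. In the last case the sign reverses.

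**What the text says about s.** Eligibility assessment by general practitioners near Lemmer (sections 6.3 and 9.2), if it applies to both groups, points to s near 0. The instruction to both sites on consecutive recruitment (6.3), the two-town base population (4.1), and inclusion of patients presenting at the hospital's X-ray facility with no limit on residence (section 3) all allow s well above 0. The documents do not settle which holds.

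**The case against.** The strongest counter-argument is that the most specific recruitment text names only general practitioners near Lemmer. If they are the source of both groups, both live largely in that area, s is near 0, and the raw difference is already the right quantity for the patients whose hospital trip the practice could replace. That would limit how far the result generalises to the stated base population; it would not bias it. This stands as a possibility, but the consecutive-recruitment instruction means it is not ensured, and without residence data nobody could verify it. A short reported trip to the hospital would hint that a patient lives near Sneek, but would not give that patient's distance to the practice.

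A second argument is that the stated secondary objective is to find determinants of satisfaction, for which the trip actually made is the natural exposure. No section names a same-patient travel contrast as a goal, and the between-group test of travel is inferred from the general reference to outcome scores in section 8.2. This stands as far as the satisfaction regressions go: actual distance should not be replaced there. Differential distance may also strongly predict which site a patient attends, and adding it to a model that contains setting could inflate variance and amplify residual confounding. None of this removes the problem for travel as an endpoint in its own right.

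A reader might also infer that the travel comparison mainly reflects where patients live. In the model that needs s above 0.5, and the documents give no residence mix. Nor can one say that the cost comparison is distorted, because no cost items are listed and travel costs are not mentioned.

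**Conclusion.** The point holds as confounding of unknown size. Travel is compared unadjusted between groups defined by recruiting site, in a two-town catchment, and the planned data cannot separate setting from residence. In the two-place model the observed difference is (1 - s) of the same-patient difference, so it ranges from fully informative at s = 0 to uninformative at s = 1. It is unbiased for Lemmer-area patients only if s is near 0. These results rest on two places, equal local trips and, for the (1 - s) form, a practice group living wholly near Lemmer.

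The reach is limited to the travel components of one secondary endpoint and, only if travel costs are included, the cost comparison. The correction is worth making because it is cheap and determines what the travel endpoint can say about substitution.

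**What to change.** - Add home postcode to the baseline data in section 6.1.3.
- For every patient, compute route distance and time from home to both the practice and the hospital. Report the within-patient difference, overall and by area of residence, as the travel result for the substitution question. The split by area is essential: in the model above a Sneek resident's difference is -(1 - a), so the overall mean is (1 - 2p)(1 - a), with p the share of the whole cohort living near Sneek. It still depends on the mix, but the mix is then visible.
- Keep distance and time actually travelled as the reported burden and as the determinant of satisfaction; do not replace them in the satisfaction regressions. Waiting and treatment time stay as between-group comparisons.
- State in section 6.3 whether hospital patients must come from general practitioners near Lemmer, and in section 8.3 whether travel costs are included. If they are, report them on the within-patient basis as well.

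The cost is one extra field with its privacy handling and a routing calculation, with no extra visits or questionnaires. The limitation is that a route from the home postcode misses the actual mode of travel and trips that do not start from home, which is a further reason to keep the reported travel data.
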